7.2.3 Intermediate Visits

Study Visit 2 (Visit 2, Day 1, POD 0)

- Perform randomization
- · Administer the study intervention, ketamine single dose or placebo. Administration of normal saline placebo is standard of care
- Assessment of opioid use and dosage assessment via subject reporting and medical record review
- Assessment of adverse events and side effects as reported by participant or observed by investigator and study team.

May 2, 2022

Version: 1.23

Document interoperative ketamine administration

Study Visit 3 (Visit 3, Day 2, POD 1)

- Participant will be asked to which treatment arm they believe they have been assigned
- VAS assessment for pelvic pain
- Subjects will complete a questionnaire packet including the EHP-30, GAD-7.and MADRS
- Assessment of opioid use and dosage assessment via subject reporting and medical record review

Page 17

- Assessment of adverse events and side effects as reported by participant or observed by investigator and study team
- If participant is still in the hospital, study staff may administer questionnaires in person or electronically via REDCap
- If the participant has already been released from the hospital, a research team member will either send the subject an electronic REDCap link to the questionnaires or call the subject to answer the questionnaires on the phone

Study Visit 4 (Visit 4, Day 28, POD 27)

- VAS assessment for pelvic pain
- Subjects will complete a questionnaire packet including the EHP-30, GAD-7 and MADRS
- Assessment of opioid use and dosage assessment
- Assessment of adverse events and side effects as reported by participant or observed by investigator and study team
- If participant is still in the hospital, study staff may administer questionnaires in person or electronically via REDCap
- If the participant has already been released from the hospital, a research team member will either send the subject an electronic REDCap link to the questionnaires or call the subject to answer the questionnaires on the phone.

Study Visit 5 (Visit 5, Day 56, POD 55)

- VAS assessment for pelvic pain
- Subjects will complete a questionnaire packet containing EHP-30, GAD-7 and MADRS
- Assessment of opioid use and dosage assessment
- Assessment of adverse events as reported by participant or observed by investigator and study
- If participant is still in the hospital, study staff may administer questionnaires in person or electronically via REDCap
- If the participant has already been released from the hospital, a research team member will either send the subject an electronic REDCap link to the questionnaires or call the subject to answer the questionnaires on the phone.

7.2.4 Final Study Visit

Study Visit 6 (Visit 6, Day 84, POD 83)

- VAS assessment for pelvic pain
- Subjects will complete a questionnaire packet including the EHP-30, GAD-7 and MADRS
- Assessment of opioid use and dosage assessment
- Assessment of adverse events as reported by participant or observed by investigator and study team

7.2.5 Withdrawal/Early Termination Visit

Participants are free to withdraw from participation in the study at any time upon request. However, participants should be counseled that they may request stopping the interventional drug but continue to be in the study. They also will be told that follow-up for adverse events is recommended for safety.

May 2, 2022 Version: 1.23

May 2, 2022 Page 18

Lost to follow-up is defined by the inability to reach a participant after a minimum of two phone calls. All attempts should be documented in the subject's medical records. If it is determined that the subject has died, the site will use permissible local methods to obtain the date and cause of death.

7.2.6 Unscheduled Visit

Unscheduled visits will be documented in the subjects' record.

7.3 Concomitant Medications, Treatments, and Procedures

All concomitant prescription medications taken during study participation will be recorded on the case report forms (CRFs). For this protocol, a prescription medication is defined as a medication that can be prescribed only by a properly authorized/licensed clinician. Medications to be reported in the CRF are concomitant prescription medications, over-the-counter medications, and non-prescription medications.

7.4 Justification for Sensitive Procedures

We will use 0.9% saline as the control. The solution Saline is a prescription medicine used for fluid and electrolyte replenishment for intravenous administration. It will serve as the placebo drug in this study. Using a placebo will help the study team better assess the role of the study drug, 0.6 mg/kg ketamine, on study outcomes.

7.5 Rescue Medications, Treatments, and Procedures

Cardiovascular side effects may be treated based on PACU clinician's decisions. If such side effects persist despite treatment, study drug may be halted.

Psychomimetic side effects will be monitored by study and PACU physicians. Such side effects may be treated with reassurance. If participants continue to complain of anxiety or dysphoria or are agitated, pharmacologic agents (such as benzodiazepines) may be administered based on clinical judgement of PACU clinicians. Benzodiazepine administration will be at discretion of PACU clinician; midazolam in titrated doses of 0.5-1 mg could be considered. If psychomimetic side effects are felt to be severe, with severe hallucinations, delusions, or agitation, study drug will be discontinued.

8 Assessment of Safety

8.1.1 Definition of Adverse Events (AE)

An **adverse event** (AE) is any symptom, sign, illness, or experience that develops or worsens in severity during the course of the study. Intercurrent illnesses or injuries should be regarded as adverse events. Abnormal results of diagnostic procedures are considered to be adverse events if the abnormality:

- results in study withdrawal
- is associated with a serious adverse event
- is associated with clinical signs or symptoms
- leads to additional treatment or to further diagnostic tests
- is considered by the investigator to be of clinical significance

8.1.2 Definition of Serious Adverse Events (SAE)

Serious Adverse Event

Adverse events are classified as serious or non-serious. A serious adverse event is any AE that is:

- fata
- life-threatening
- requires or prolongs hospital stay
- results in persistent or significant disability or incapacity
- a congenital anomaly or birth defect
- an important medical event

May 2, 2022 Version: 1.23 Page 19

Important medical events are those that may not be immediately life threatening but are clearly of major clinical significance. They may jeopardize the subject and may require intervention to prevent one of the other serious outcomes noted above. For example, drug overdose or abuse, a seizure that did not result in in-patient hospitalization, or intensive treatment of bronchospasm in an emergency department would typically be considered serious.

All adverse events that do not meet any of the criteria for serious should be regarded as **non-serious adverse events**.

8.1.3 Definition of Unanticipated Problems (UP) Involving Risk to Subjects or Others

Any incident, experience, or outcome that meets all the following criteria:

- Unexpected in nature, severity, or frequency (i.e., not described in study-related documents such as the IRB-approved protocol or consent form, the investigators brochure, etc.)
- Related or possibly related to participation in the research (i.e., possibly related means there is a reasonable possibility that the incident experience, or outcome may have been caused by the procedures involved in the research)
- Suggests that the research places subjects or others at greater risk of harm (including physical, psychological, economic, or social harm).

8.2 Classification of an Adverse Event

8.2.1 Severity of Event

For AEs not included in the protocol defined grading system, the following guidelines will be used to describe severity.

- Mild Events require minimal or no treatment and do not interfere with the participant's daily activities
- **Moderate** Events result in a low level of inconvenience or concern with the therapeutic measures. Moderate events may cause some interference with functioning.
- **Severe** Events interrupt a participant's usual daily activity and may require systemic drug therapy or other treatment. Severe events are usually potentially life-threatening or incapacitating.

8.2.2 Study Agent

The clinician's assessment of an AE's relationship to study drug is part of the documentation process, but it is not a factor in determining what is or is not reported in the study. If there is any doubt as to whether a clinical observation is an AE, the event should be reported. All AEs must have their relationship to study agent assessed. In a clinical trial, the study product must always be suspect. To help assess, the following guidelines are used.

For all collected AEs, the clinician who examines and evaluates the participant will determine the AE's causality based on temporal relationship and his/her clinical judgment. The degree of certainty about causality will be graded using the categories below.

- Definitely Related There is clear evidence to suggest a causal relationship, and other possible
 contributing factors can be ruled out. The clinical event, including an abnormal laboratory test result,
 occurs in a plausible time relationship to drug administration and cannot be explained by concurrent
 disease or other drugs or chemicals. The response to withdrawal of the drug (dechallenge) should
 be clinically plausible. The event must be pharmacologically or phenomenologically definitive, with
 use of a satisfactory rechallenge procedure if necessary.
- Probably Related There is evidence to suggest a causal relationship, and the influence of other
 factors is unlikely. The clinical event, including an abnormal laboratory test result, occurs within a
 reasonable time after administration of the drug, is unlikely to be attributed to concurrent disease

May 2, 2022 Version: 1.23

or other drugs or chemicals, and follows a clinically reasonable response on withdrawal (dechallenge). Rechallenge information is not required to fulfill this definition.

- Possibly Related There is some evidence to suggest a causal relationship (e.g., the event occurred within a reasonable time after administration of the trial medication). However, other factors may have contributed to the event (e.g., the participant's clinical condition, other concomitant events). Although an AE may rate only as "possibly related" soon after discovery, it can be flagged as requiring more information and later be upgraded to "probably related" or "definitely related," as appropriate.
- Unlikely to be related A clinical event, including an abnormal laboratory test result, whose temporal relationship to drug administration makes a causal relationship improbable (e.g., the event did not occur within a reasonable time after administration of the trial medication) and in which other drugs or chemicals or underlying disease provides plausible explanations (e.g., the participant's clinical condition, other concomitant treatments).
- Not Related The AE is completely independent of study drug administration, and/or evidence
 exists that the event is definitely related to another etiology. There must be an alternative, definitive
 etiology documented by the clinician.

8.2.3 Expectedness

The principal investigator will be responsible for determining whether an AE is expected or unexpected. An AE will be considered unexpected if the nature, severity, or frequency of the event is not consistent with the risk information previously described for the study agent.

8.3 Time Period and Frequency for Event Assessment and Follow-Up

The occurrence of an AE or SAE may come to the attention of study personnel during study visits and interviews of a study participant presenting for medical care, or upon review by a study monitor. All AEs including local and systemic reactions not meeting the criteria for SAEs will be captured on the appropriate CRF. Information to be collected includes event description, time of onset, clinician's assessment of severity, relationship to study product (assessed only by those with the training and authority to make a diagnosis), and time of resolution/stabilization of the event. All AEs occurring while on study must be documented appropriately regardless of relationship. All AEs will be followed to adequate resolution.

Any medical condition that is present at the time that the participant is screened will be considered as baseline and not reported as an AE. However, if the study participant's condition deteriorates at any time during the study, it will be recorded as an AE. UPs will be recorded in the data collection system throughout the study.

Changes in the severity of an AE will be documented to allow an assessment of the duration of the event at each level of severity to be performed. AEs characterized as intermittent require documentation of onset and duration of each episode.

The PI will record all reportable events with start dates occurring any time after informed consent is obtained until 7 (for non-serious AEs) or 30 days (for SAEs) after the last day of study participation. At each study visit, the investigator will inquire about the occurrence of AE/SAEs since the last visit. Events will be followed for outcome information until resolution or stabilization.

All unresolved adverse events should be followed by the investigator until the events are resolved, the subject is lost to follow-up, or the adverse event is otherwise explained. At the last scheduled visit, the investigator should instruct each subject to report any subsequent event(s) that the subject, or the subject's personal physician, believes might reasonably be related to participation in this study. The investigator should notify the study sponsor of any death or adverse event occurring at any time after a subject has discontinued or terminated study participation that may reasonably be related to this study. The sponsor should also be notified if the investigator should become aware of the development of cancer or of a congenital anomaly in a subsequently conceived offspring of a subject that has participated in this study.

May 2, 2022 Version: 1.23

Page 21

8.4 Notifying the IRB

8.4.1 Adverse Event Reporting

The PI will record all reportable events with start dates occurring any time after informed consent is obtained until 7 (for non-serious AEs) or 30 days (for SAEs) after the last day of study participation.

At each contact with the subject, the investigator must seek information on adverse events by specific questioning and, as appropriate, by examination. Information on all adverse events should be recorded immediately in the source document, and also in the appropriate adverse event module of the case report form (CRF). All clearly related signs and symptoms should be recorded in the source document, though should be grouped under one diagnosis.

All adverse events occurring during the study period must be recorded. The clinical course of each event should be followed until resolution, stabilization, or until it has been determined that the study treatment or participation is not the cause. Serious adverse events that are still ongoing at the end of the study period must be followed up to determine the final outcome. Any serious adverse event that occurs after the study period and is considered to be definitely and probably related to the study treatment or study participation should be recorded and reported immediately.

8.4.2 Serious Adverse Event Reporting

Investigators and the protocol sponsor must conform to the adverse event reporting timelines, formats, and requirements of the various entities to which they are responsible, but at a minimum those events that must be reported within 5 or 10 days of PI notification are those that are:

- related to study participation,
- unexpected, and
- Harmful or have the potential to cause harm

The study clinician will complete a SAE Form within the following timelines:

- All deaths and immediately life-threatening events, related and unrelated, will be recorded on the SAE Form and submitted within 24 hours of site awareness.
- Other SAEs will be submitted within 72 hours of site awareness.

This information should be reported to the PI and to the DSMC. All SAEs will be followed until satisfactory resolution or until the site investigator deems the event to be chronic or the adherence to be stable. Other supporting documentation of the event may be requested and should be provided as soon as possible.

As a follow-up to the initial report, within the following 48 hours of awareness of the event, the investigator shall provide further information, as applicable, on the unanticipated event or the unanticipated problem in the form of a written narrative. This should include a copy of the completed Unanticipated Problem form, and any other diagnostic information that will assist the understanding of the event. Significant new information on ongoing unanticipated adverse effects shall be provided promptly.

Adverse events that do not fit the above immediately reportable criteria must still be reported to the IRB at each annual review, either in a summary or tabular format.

8.4.3 Unanticipated Problem Reporting

Incidents or events that meet the OHRP criteria for UPs require the creation and completion of an UP report form. It is the site investigator's responsibility to report UPs to their IRB and to the Data Coordinating Center (DCC)/study sponsor. The UP report will include the following information:

- Protocol identifying information; protocol title and number. Pl's name, and the IRB project number:
- A detailed description of the event, incident, experience, or outcome;
- An explanation of the basis for determining that the event, incident, experience, or outcome represents an UP;

May 2, 2022 Page 22

Version: 1.23

 A description of any changes to the protocol or other corrective actions that have been taken or are proposed in response to the UP.

To satisfy the requirement for prompt reporting, UPs will be reported using the following timeline:

- UPs that are SAEs will be reported to the IRB 5 or 10 days of the investigator or the study team becoming aware of the event. Unexpected death of unknown causality and any event requiring immediate intervention to prevent subject harm requires 5 calendar days.
- Any other UP will be reported to the IRB within 5 or 10 days of the investigator or the study team becoming aware of the problem.
- All UPs should be reported to appropriate institutional officials (as required by an institution's written reporting procedures), the supporting agency head (or designee), and OHRP within 5 or 10 days of the IRB's receipt of the report of the problem from the investigator and the study team.

8.4.4 Reportable Events

The reportable events noted above will be reported to the IRB using the form: "Reportable Event Form" or as a written report of the event (including a description of the event with information regarding its fulfillment of the above criteria, follow-up/resolution and need for revision to consent form and/or other study documentation). Copies of each report and documentation of IRB notification and receipt will be kept in the Clinical Investigator's study file. The Principal Investigator is responsible for reporting all unexpected problems involving risk to participants or others.

8.5 Safety Oversight

It is the responsibility of the Principal Investigator to oversee the safety of the study at the site. This safety monitoring will include careful assessment and appropriate reporting of adverse events as noted above, as well as the construction and implementation of a site data and safety-monitoring plan. Medical monitoring will include a regular assessment of the number and type of serious adverse events. The data safety monitoring plan is as follows:

The individuals responsible for data safety and monitoring will be [name] and [name]. A conflict of interest will be avoided by study team's full disclosure of conflicts as per NYULH standards.

Quality control will include regular data verification and protocol compliance checks by [name].

[name] will complete quarterly reports detailing the study progress and subject status, any adverse events, and any protocol deviations. Specific data to be reviewed in the quarterly reports include: pelvic pain scores, general anxiety scores, depression scores, opioid use and dosage, and any adverse events reported to or observed by the study team including but not limited to side effects of the study drug. Protocol adherence (specifically, the participants' completing the assigned surveys) will be monitored by [name], Research Coordinator. All other aspects of protocol compliance will be reviewed by [name].

Throughout the study, the study team will monitor the participants for adverse events. Events determined by the Principal Investigator (PI) to be unanticipated problems involving risks to subjects or others (UPIRTSOs) will be reported by the PI to the IRB within 10 days per policy. Adverse events that are determined by the PI to not be UPIRTSOs will be reported per IRB policy at the time of continuing review. Reference section 5.8 for specific stop criteria to be used by the study team.

All study staff members will be informed by [name] about any UPIRTSOs. If any protocol changes are needed, the PI will submit a modification request to the IRB (and VA R&D if applicable). Protocol changes will not be implemented prior to IRB approval unless necessary to eliminate apparent immediate hazards to the research subjects. In such a case, the IRB will be promptly informed of the change following implementation (within 10 working days). The Study team will also submit an annual report with the Continuing Review Submission.

May 2, 2022 Version: 1.23

2, 2022 Page 23

Statistical review of the study will be conducted by [name] at the end of all study visits for all subjects. Interim analyses will be performed by [name] to assess equity. If inequity occurs, consideration will be given to stopping the study early. In the event of early stopping of the study, the IRB will be promptly notified.

9 Clinical Monitoring

Clinical site monitoring is conducted to ensure that the rights and well-being of human subjects are protected, that the reported trial data are accurate, complete, and verifiable, and that the conduct of the trial is in compliance with the currently approved protocol/amendment(s), with GCP, and with applicable regulatory requirement(s). The completeness, accuracy and consistency of the data, and adherence to ICH Good Clinical Practice guidelines will be followed.

10 Statistical Considerations

10.1 Statistical Hypotheses

The primary outcome will be the assessment of postoperative pain using the Visual Analogue Scale (VAS) between the ketamine and placebo arms at enrollment date, POD 1, POD 27, POD 55, and POD 83. We hypothesize that subjects who receive ketamine will have lower postoperative pain scores at all time points than those who receive placebo. Secondary outcomes include changes in opioid use between the ketamine and control arms, as well as changes in Endometriosis Health Profile-30, General Anxiety Disorder-7 (GAD-7), and Montgomery-Asberg Depression Rating Scales (MADRS). We hypothesize that subjects who receive ketamine will have decreased opioid use, as well as lower scores on the mood and quality of life scales above than those who receive placebo.

10.2 Analysis Datasets

The study dataset consists of 30 subjects; 15 of whom will be randomized to receive a sub anesthetic single bolus of ketamine (0.6 mg/kg) following robotic removal of endometriosis and 15 of whom will be randomized to receive an equal volume saline bolus as control. All analyses will be treated as intention to treat based on the randomization of study subjects to either the ketamine arm or placebo arm.

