4.1 Description of Study Design

This is a phase 1 randomized, double-blind, placebo-controlled, two-arm parallel, single-center study.

30 subjects (15 in each arm) will be accrued. Randomization lists will be sent only to the study physician administering study drug. Participant and assessor of outcome measures will be blinded. The surgeon, anesthesiologist, and the research team members conducting the follow up visits will not know which group the subjects are assigned to. Only the physician administrating the study will be aware of whether ketamine or placebo is administered, and this provider will not be a part of any outcome measure data collection. The investigators conducting and reviewing the outcome measures will be blinded.

Adult women, aged 18-65, with chronic pelvic pain (defined as moderate to severe self-report > 6 months) will be screened for eligibility to participate in this study. Prospective subjects will be recruited, screened, and consented prior to surgery. On the day of the surgery, Eligible subjects will be randomized to one of the two groups in a 1:1 ratio to receive either intravenously (IV) ketamine (0.6 mg/kg) or matching equal dose of placebo. Subjects will receive either the study drug or placebo while recovering in the post anesthesia care unit (PACU) on the day of the surgery after subject has been deemed to be stable

May 2, 2022 Version: 1.23

2, 2022 Page 9

(hemodynamically stable, awake). The study drug or placebo will be administered by study physicians who are anesthesiologists. The study physician will administer the study intervention via an intravenous pump to deliver 0.6 mg/kg ketamine or equal volume saline over at least 30 minutes.

Participation in the study will not alter the subject's surgical or anesthetic care, post-anesthetic care, or standard of care on the floor. All subjects will also receive standard post-anesthetic monitoring and care, as well as routine care after transferring out of the PACU. There is no restriction on the use of other analgesics throughout this study. Subjects are followed, and endpoints (see below) are collected from subject reports as well as from medical charts (opioid use).

Patient demographics recorded include age, date of birth, race, MRN, gender, ethnicity, participant enrollment location, zip code, and disease site.

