7. Assessment of Adverse Events: Assessment of adverse events as reported by participant or observed by investigator and study team The assessment of adverse events will be completed at the enrollment date, POD 1, POD 27, POD 55 and POD 83. Events will be recorded via study database.

5 Study Enrollment and Withdrawal

Prospective subjects will be screened, recruited, and consented prior to their surgery date. Participants will be screened during the surgical consult by the study surgeon, who may give potential participants a one-pager with key information on the study. Should the patient meet the inclusion criteria (see below) and are interested in participating, they will be referred to (their information will be shared with) a clinical research coordinator on the study team who will call prospective subjects or arrange a video conference session (WebEx only). Eligible patients will be invited to participate in the study and the research coordinator will answer any outstanding questions and begin the informed consent process.

The subject will remotely receive a link to the informed consent, sign, and return informed consent document through a REDCap link. The link to the REDCap e-consent will be submitted to the IRB via modification following initial approval. The study team will not use the REDCap e-consent until it has been IRB approved. The prospective subject will be emailed a copy of the informed consent form. Once informed consent is given, the study team member will provide the participant with information regarding the next steps for participation. Consent may be obtained up to two months before surgery at the earliest, but will occur no less than 2 days before a subject's surgery at the latest..

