- Any clinical adverse event (AE), laboratory abnormality, or other medical condition or situation occurs such that continued participation in the study would not be in the best interest of the
- The participant meets an exclusion criterion (either newly developed or not previously recognized) before surgery that precludes further study participation.

Criteria for discontinuing study intervention includes but not limited to:

- Allergic reaction thought to be related to study drug
- Uncontrolled hypertension, hypotension, or arrhythmia thought to be related to study drug
- Severe psychomimetic side effects
- Medical events/logistical reasons not related to study therapy

Study physician will be responsible for determining whether study interventions will be discontinued, based on his or her clinical judgement. In the case of cardiovascular side effects, if such side effects persist despite treatment based on PACU clinician's decisions, study drug may be discontinued. The reason for the dose discontinuation should be documented.

Psychomimetic side effects will be monitored by study and PACU physicians. Such side effects may be treated with reassurance. If participants continue to complain of anxiety or dysphoria or are agitated, pharmacologic agents (such as benzodiazepines) may be administered based on clinical judgement of PACU clinicians. If psychomimetic side effects are felt to be severe, with severe hallucinations, delusions, or agitation, study drug will be discontinued.

Additionally, in the event of any discontinuation of study intervention, with consent, participants will continue with the completion of remaining study visits.

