6.1.5 Dosing and Administration

Single bolus ketamine: For the single bolus dose arm, ketamine at a dose of 0.6 mg/kg will be administered while the participant is recovering in the PACU on the day of surgery. The study drug will be administered over at least 30 minutes at one time point and will be administered after subject has been deemed to be stable (hemodynamically stable, awake) by the study team on POD 0.

Control/Placebo: Participants randomized into this group will receive matching volume of saline infusion in the PACU over at least 30 minutes at one time point (no ketamine).

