10.3.4 Safety Analyses

Descriptive statistics will be used to summarize side effects of the intervention at POD 0, POD 1, and POD 27 as well as adverse events as reported by participant or observed by the investigator at POD 1, POD 27, POD 55, and POD 83.

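### Safety falls under the blanket intention-to-treat rule: the plan defines no safety set of infused women and no rule that events must begin after the infusion starts

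*Combined protocol and SAP*

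**What the plan says.** **Population.** Section 10.2 (Analysis Datasets) says: "All analyses will be treated as intention to treat based on the randomization of study subjects to either the ketamine arm or placebo arm". Section 10.3.4 (Safety Analyses) says: "Descriptive statistics will be used to summarize side effects of the intervention at POD 0, POD 1, and POD 27". It adds adverse events at POD 1, 27, 55 and 83. It names no population and sets no condition on when an event began. Sections 10.3.8 and 10.3.10 plan no further analyses, and no safety set is defined elsewhere.

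**From randomization to dosing.** Section 4.1: "On the day of the surgery, Eligible subjects will be randomized to one of the two groups in a 1:1 ratio". Section 6.1.5 says the study drug "will be administered after subject has been deemed to be stable (hemodynamically stable, awake) by the study team on POD 0".

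**Recording of events.** Section 8.3: "The PI will record all reportable events with start dates occurring any time after informed consent is obtained". The introduction to Section 5 adds: "Consent may be obtained up to two months before surgery at the earliest". Section 8.3 also has the time of onset recorded and asks at each visit about events since the previous one. Section 8.2.2 requires a causality grade for every adverse event.

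**Which adverse-event assessments exist.** Section 4.2.2 lists enrollment and POD 1, 27, 55 and 83. The visit descriptions in Section 7.2 and the schedule in Section 20 have all of these and POD 0 as well. Section 10.3.4 summarizes neither enrollment nor POD 0.

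**The concern.** Intention to treat protects the efficacy comparison. In a safety table it answers a different question from the one Section 3.2 asks, which is the incidence of side effects. A woman who never received the infusion cannot have a side effect of it, yet she would count in the ketamine denominator and pull the rate down. A woman given the other arm's infusion by mistake would carry her events to the arm she was assigned to.

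The missing onset rule matters because the infusion follows general anesthesia and surgery on the same day. Section 2.4.1 itself warns that nausea and vomiting may come from the recent anesthetic and ketamine together. Visit 2 in Section 7.2.3 also asks for ketamine given in connection with the operation to be documented. An effect that began before the study infusion could be entered at POD 0, and nothing in Section 10.3.4 sets it aside.

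Section 2.4.1 says side effects typically end 30 minutes after the infusion. The assessment most likely to catch acute adverse events is therefore the POD 0 one, which Section 10.3.4 leaves off its adverse-event list.

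**Working it through.** **The plan's own figure.** The only calculated figure is the power in Section 10.4: 80% at an effect size of 1.1 with 15 per arm, by two-sided Wilcoxon test on normal data. Simulation (40,000 trials) gives 79.7% with the exact or continuity-corrected test and 81.1% without correction, so it reproduces. It concerns the VAS. Safety is descriptive and does not affect it.

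**Inputs for dilution.**
- Arm size: 15. Section 4.1: "30 subjects (15 in each arm) will be accrued".
- Illustrative rate among infused women: 12%, the approximate emergence-reaction rate in Section 2.4.1. That section does not tie it to 0.6 mg/kg.
- k, the number randomized to ketamine but not infused: not in the documents. I assume 0 to 3.

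Formula: rate as randomized = rate among infused × (15 − k)/15.

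| k | Calculation | Rate as randomized |
|---|---|---|
| 0 | 12% × 15/15 | 12.0% |
| 1 | 12% × 14/15 | 11.2% |
| 2 | 12% × 13/15 | 10.4% |
| 3 | 12% × 12/15 | 9.6% |

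Each undosed woman takes off 0.8 points. On a safety set of infused women the rate stays at 12% for every k.

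**Scale.** Two events in 15 is 13.3%, exact 95% interval 1.7% to 40.5%. Removing two undosed women gives 2 in 13, or 15.4%, interval 1.9% to 45.4%. The shift of 2.1 points is far smaller than either interval.

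**Wrong-arm events.** One placebo-assigned woman given ketamine in error, with one event, would add 1/15 = 6.7 points to the placebo rate. This is hypothetical; the documents give no reason to expect it.

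**Pre-infusion events on POD 0.** Let b be the assumed chance of such an event, equal in both arms and independent of later events. Suppose 12% of ketamine women and no placebo women have an event after infusion starts. If both kinds are pooled:

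- ketamine: 1 − (1 − 0.12)(1 − b)
- placebo: b
- difference: 0.12 × (1 − b)

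| b (assumed) | Ketamine | Placebo | Difference |
|---|---|---|---|
| 5% | 16.4% | 5% | 11.4 points |
| 10% | 20.8% | 10% | 10.8 points |
| 20% | 29.6% | 20% | 9.6 points |
| 30% | 38.4% | 30% | 8.4 points |

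Both rates rise and the 12-point difference shrinks.

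**The POD 0 assessment.** If POD 1 in Section 10.3.4 means events reported at that visit, Section 8.3's look-back reaches only to the POD 0 assessment. An adverse event already taken down at POD 0 would then fall outside the summary. If it means all events up to POD 1, surgical and anesthetic events enter as well. The text does not choose between these readings.

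**The case against.** The strongest case against is that little here will move a number. Safety is descriptive, the trial is a pilot, and intervals at 15 per arm swamp any plausible dilution. Randomization and infusion fall within one visit, so few women should be lost between them. Dose tracking (6.1.8), drug reconciliation (6.2) and causality grading would help reveal an undosed woman, a misdosed woman or an unrelated event. All of that stands and keeps the point modest. It does not change what Section 10.2 says.

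A reader might also infer more than the documents support:

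- **That side-effect rates are in fact diluted.** This needs at least one undosed woman, and k = 0 is possible. The allowance in Section 5.6 of about 50 enrolled to keep 30 is not split into losses before and after randomization, so it does not supply k.
- **That the discontinuation criteria in Section 5.7.1 create undosed women.** The item "Medical events/logistical reasons not related to study therapy" is a reason to discontinue the intervention, which ordinarily means it has started. A woman whose infusion is stopped has been exposed and belongs in a safety set. The route to an undosed woman is the PACU stability condition.
- **That up to two months of events before surgery enter the side-effect tables.** Recording does begin at consent, but side effects are a separate questionnaire that starts at POD 0. The adverse-event summary starts at POD 1. The exposed period is POD 0 before the infusion.
- **That pre-infusion events understate ketamine's rate.** They raise both arms' rates alike and blur the contrast. They do not favor an arm.

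**Conclusion.** The point holds as a defect of specification. Section 10.2 is a positive rule covering every analysis, Section 10.3.4 makes no exception, and the dosing condition makes a randomized but undosed woman possible. Followed literally, the plan would understate the ketamine side-effect rate by 0.8 points per undosed woman at a true rate of 12%, and by nothing if all are infused. This rests on an assumed k, an illustrative 12% and a denominator of 15. Section 5.7.2 allows replacements, so the denominator may itself differ.

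The missing onset rule is a separate weakness: noise in both arms from POD 0 events before the infusion, of a size the documents do not allow one to estimate. The omission of the POD 0 adverse-event assessment from the summary is an inconsistency on the face of the text. The side-effect questionnaire, which is summarized at POD 0, partly covers it.

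The correction should be made, because it is standard and cheap, and choosing the safety population after the data are seen invites doubt. It does not threaten the primary analysis.

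**What to change.** 1. In Section 10.2, limit the intention-to-treat sentence to efficacy.
2. Add a safety set: everyone who received any amount of study infusion, grouped by the infusion actually received.
3. In Section 10.3.4, tabulate side effects and adverse events with onset at or after the start of infusion, POD 0 included. List earlier events separately.
4. Reconcile Sections 4.2.2, 7.2, 10.3.4 and 20 on which adverse-event assessments exist and which are summarized.

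The cost is a few sentences and one check. Section 8.3 has event onset recorded, but no section says that infusion start time is. Confirm that the medical record or REDCap captures it, and that onset on POD 0 is taken to clock time.
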